9.1.3 Efficacy

No clinical efficacy data will be obtained in the study.

9.2 Secondary Endpoints and Assessment Methods

9.2.1 Safety

There are no secondary objectives for safety.

9.2.2 Immunogenicity

9.2.2.1 Immunogenicity Endpoints

The following serological endpoints will be assessed.

- 1) Meningococcal serogroups A, C, Y, and W antibody titers $\geq 1:8$ measured by hSBA 30 days after the second dose of MenACYW conjugate vaccine or MENVEO® (Group 1 vs Group 2)
- 2) 30 days after the second vaccination at 12 to 13 months of age with MenACYW conjugate vaccine or MENVEO® (Group 1 and Group 2):
 - hSBA meningococcal serogroups A, C, Y, and W antibody titers
 - Geometric mean titers (GMTs) with 95% CI
 - Titer distribution and reverse cumulative distribution curves (RCDCs)
 - Percentage of subjects with titer ≥ 4 -fold rise from pre-vaccination to post-vaccination and 95% CI
- 3) 30 days after the first vaccination at 6 to 7 months of age with MenACYW conjugate vaccine or MENVEO® (Group 1 and Group 2):
 - hSBA meningococcal serogroups A, C, Y, and W antibody titers
 - GMTs with 95% CI
 - Titer distribution and RCDCs
 - Percentage of subjects with titer ≥ 4 -fold rise from pre-vaccination to post-vaccination and 95% CI
 - Percentage of subjects with hSBA vaccine seroresponse and 95% CI
- 4) 6 months after the first vaccination at 6 to 7 months of age with MenACYW conjugate vaccine or MENVEO® (Group 1 and Group 2):
 - hSBA meningococcal serogroups A, C, Y, and W antibody titers
 - GMTs with 95% CI
 - Titer distribution and RCDCs
 - Percentage of subjects with titer ≥ 4 -fold rise from pre-vaccination to post-vaccination and 95% CI
 - Percentage of subjects with hSBA vaccine seroresponse and 95% CI

- 5) 30 days after the second vaccination at 20 to 23 months of age with MenACYW conjugate vaccine or Menactra® (Group 3 and Group 4):
 - hSBA meningococcal serogroups A, C, Y, and W antibody titers
 - GMTs with 95% CI
 - Titer distribution and RCDCs
 - Percentage of subjects with titer \geq 4-fold rise from pre-vaccination to post-vaccination and 95% CI
 - Percentage of subjects with hSBA vaccine seroresponse and 95% CI

9.2.2.2 Immunogenicity Assessment Methods

The immunogenicity assessment methods for the secondary endpoints are the same as those presented in [Section 9.1.2.2](#).

9.2.3 Efficacy

No clinical efficacy data will be obtained in the study.

9.3 Observational Endpoints and Assessment Methods

9.3.1 Immunogenicity

There are no observational objectives for immunogenicity in this study.

9.3.2 Safety

9.3.2.1 Safety Definitions

The following definitions are taken from the ICH E2A Guideline for Clinical Safety Data Management: Definitions and Standards for Expedited Reporting.

Adverse Event (AE):

An AE is any untoward medical occurrence in a patient or in a clinical investigation subject administered a medicinal product and which does not necessarily have a causal relationship with this treatment. An AE can therefore be any unfavorable and unintended sign (including an abnormal laboratory finding, for example), symptom or disease temporally associated with the use of a medicinal product, whether or not considered related to the medicinal product.

Therefore an AE may be:

- A new illness

- The worsening of a pre-existing condition
- An effect of the vaccination, including the comparator
- A combination of the above

All AEs include serious and non-serious AEs.

Surgical procedures are not AEs; they are the actions taken to treat a medical condition. It is the condition leading to the action taken that is the AE (if it occurs during the study period).

Pre-existing medical conditions are not to be reported as AEs. However, if a pre-existing medical condition worsens following study interventions in frequency or intensity, or if according to the Investigator there is a change in its clinical significance, this change should be reported as an AE (exacerbation). This applies equally to recurring episodes of pre-existing conditions (e.g., asthma) if the frequency or intensity increases post-vaccination.

Serious Adverse Event (SAE):

Serious and *severe* are not synonymous. The term *severe* is often used to describe the intensity of a specific event as corresponding to Grade 3. This is not the same as *serious* which is based on subject / event outcome or action criteria usually associated with events that pose a threat to a subject's life or functioning. Seriousness, not severity, serves as a guide for defining regulatory reporting obligations.

An SAE is any untoward medical occurrence that at any dose

- Results in death
- Is life-threatening^a
- Requires inpatient hospitalization or prolongation of existing hospitalization^b
- Results in persistent or significant disability / incapacity^c
- Is a congenital anomaly / birth defect
- Is an important medical event (IME)

^a The term “life-threatening” refers to an event in which the subject was at risk of death at the time of the event; it does not refer to an event which hypothetically might have caused death if it were more severe.

^b All medical events leading to hospitalizations will be recorded and reported as SAEs, with the exception of: hospitalization planned before inclusion into the study or outpatient treatment with no hospitalization.

^c “Persistent or significant disability or incapacity” means that there is a substantial disruption of a person’s ability to carry out normal life functions.

Medical and scientific judgment should be exercised in deciding whether expedited reporting is appropriate in other situations, such as IMEs that may not be immediately life-threatening or result in death or hospitalization but may jeopardize the health of the subject or may require intervention to prevent one of the other outcomes listed in the definition above. These IMEs should also usually be considered serious. Examples of such events include allergic bronchospasm requiring intensive treatment in an emergency room or at home, blood dyscrasias or convulsions that do not result in inpatient hospitalization, or the development of drug dependency or drug abuse, new-onset diabetes, or autoimmune disease.

Adverse Reaction:

All noxious and unintended responses to a medicinal product related to any dose should be considered adverse reactions (AR).

(The phrase “responses to a medicinal product” means that a causal relationship between a medicinal product and an AE is at least a reasonable possibility)

The following additional definitions are used by Sanofi Pasteur:

Immediate Event/Reaction:

Immediate events are recorded to capture medically relevant unsolicited systemic AEs (including those related to the product administered) that occur within the first 30 minutes after vaccination.

Solicited Reaction:

A solicited reaction is an “expected” adverse reaction (sign or symptom) observed and reported under the conditions (nature and onset) prelisted in the protocol and CRB (e.g., injection site tenderness or irritability occurring between D0 and D07 after vaccination).

By definition, solicited reactions are to be considered as being related to the product administered.

For injectable vaccines, solicited reactions can either be solicited injection site reactions or solicited systemic reactions.

The assessment of these reactions by the investigator is mandatory.

Unsolicited AE / AR:

An unsolicited AE is an observed AE that does not fulfill the conditions prelisted in the CRB in terms of diagnosis and/or onset window post-vaccination. For example, if vomiting between D0 and D07 is a solicited reaction (i.e., prelisted in the protocol and CRB), then a vomiting starting on D07 is a solicited reaction, whereas vomiting starting on D08 post-vaccination is an unsolicited AE. Unsolicited AEs includes both serious (SAEs) and non-serious unsolicited AEs.

Injection Site Reaction:

An injection site reaction is an AR at and around the injection site. Injection site reactions are commonly inflammatory reactions. They are considered to be related to the product administered.

Systemic AE:

Systemic AEs are all AEs that are not injection or administration site reactions. They therefore, include systemic manifestations such as vomiting, fever, as well as localized or topical manifestations that are not associated with the vaccination or administration site (e.g., erythema that is localized but that is not occurring at the injection site).

Adverse Event of Special Interest (AESI):

An AESI is an event for which ongoing monitoring and rapid communication by the Investigator to the Sponsor must be done. Such an event might warrant further investigation in order to characterize and understand it. Depending on the nature of the event, rapid communication by the study Sponsor to other parties (e.g., regulators) might also be warranted.

Medically-Attended Adverse Event (MAAE)

An MAAE is defined, for the purpose of this study, as a new onset of a condition that prompts the subject or subject's parent/guardian to seek unplanned medical advice at a health care provider's office or Emergency Department. This definition excludes pre-planned medical office visits for routine pediatric check-ups or follow-up visits of chronic conditions with an onset prior to entry in the study. Health care provider contact made over the phone or by email will be considered a physician office visit for the purpose of MAAE collection. The outcome of the health care provider contact (whether it results in a prescription or not) will not be considered as a basis for reporting the event as an MAAE and all contacts should be reported. Sufficient data should be collected for the event to allow an assessment of the causality and diagnosis, if possible.

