The routine pediatric vaccines recommended at 6 months of age will be given as per standard of care during the first study visit (Visit 1) along with the corresponding study vaccine. The dose of Prevnar 13® and Hib (for children vaccinated with monovalent Hib vaccine at 2, 4, and 6 months of age) recommended in the second year of life may be given as per standard of care at the last study visit after completing all the study procedures (Visit 4). Routine pediatric vaccines recommended at 6 months of age and the dose of Prevnar 13® recommended in the second year of life will not be provided by the Sponsor but procured by the sites as per their standard practices.

Blood Sampling

All subjects in Group 1 and Group 2 will provide 3 blood samples for immunogenicity assessment:

- A blood sample before the first study vaccination at Visit 1 (all subjects)
- A blood sample 30 days after administration of the first dose of MenACYW conjugate vaccine or MENVEO® at Visit 2 (only from approximately the first 50% of the subjects in Group 1 and Group 2)
- A blood sample before the 12-month vaccination at Visit 3 (only from the remaining approximately 50% of subjects in Group 1 and Group 2, who did not have a blood draw at Visit 2)
- A blood sample 30 days after administration of the second dose of MenACYW conjugate vaccine or MENVEO® at Visit 4 (all subjects in Group 1 and Group 2)

All subjects in Group 3 and Group 4 will provide 2 blood samples for immunogenicity assessment:

- A blood sample before the first study vaccination at Visit 1
- A blood sample 30 days after administration of the second dose of MenACYW conjugate vaccine or Menactra® at Visit 3

Collection of Safety Data

Immediate unsolicited systemic AEs will be collected within 30 minutes after each vaccination. Solicited AEs will be collected from Day (D) 0 to D07 after each vaccination; unsolicited AEs will be collected from D0 after each vaccination to the next study visit; SAEs (including adverse events of special interest [AESIs]) and medically attended adverse events (MAAEs) will be collected throughout the study from Visit 1 (first vaccination visit) until the end of the 6-month follow up period after the last vaccinations.

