9.3.2.2 Safety Endpoints

The following endpoints will be used for all subjects:

- Occurrence, nature (Medical Dictionary for Regulatory Activities [MedDRA] preferred term), duration, intensity, relationship to vaccination, and whether the event led to early termination from the study, of any unsolicited systemic AEs reported within 30 minutes after each vaccination.
- Occurrence, time of onset, number of days of occurrence, intensity, action taken, and whether the reaction led to early termination from the study, of solicited (prelisted in the subject's diary card and CRB) injection site reactions occurring up to D07 after each vaccination.
- Occurrence, time of onset, number of days of occurrence, intensity, action taken, and whether the reaction led to early termination from the study, of solicited (prelisted in the subject's diary card and CRB) systemic reactions occurring up to D07 after each vaccination.

- Occurrence, nature (MedDRA preferred term), time of onset, duration, intensity, action taken, relationship to vaccination, and whether the event led to early termination from the study, of unsolicited AEs up to D30 after each vaccination.
- Occurrence, nature (MedDRA preferred term), time of onset, duration, seriousness criteria, relationship to vaccination, outcome, and whether the event led to early termination from the study, of SAEs (including AESIs) throughout the trial from Visit 1 up to the 6 month follow-up contact after the last vaccination.
- Occurrence, nature (MedDRA preferred term), time of onset, duration, intensity, action taken, relationship to vaccination, and whether the event led to early termination from the study for MAAEs throughout the trial from Visit 1 up to the 6 month follow-up contact after the last vaccination.

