Unsolicited AE / AR:

An unsolicited AE is an observed AE that does not fulfill the conditions prelisted in the CRB in terms of diagnosis and/or onset window post-vaccination. For example, if vomiting between D0 and D07 is a solicited reaction (i.e., pre-listed in the protocol and CRB), then vomiting starting on D07 is a solicited reaction, whereas vomiting starting on D08 post-vaccination is an unsolicited AE. Unsolicited AEs includes both serious (SAEs) and non-serious unsolicited AEs.

Injection Site Reaction:

An injection site reaction is an AR at and around the injection site. Injection site reactions are commonly inflammatory reactions. They are considered to be related to the product administered.

Systemic AE:

Systemic AEs are all AEs that are not injection or administration site reactions. They therefore include systemic manifestations such as vomiting, fever, as well as localized or topical manifestations that are not associated with the vaccination or administration site (e.g., erythema that is localized but that is not occurring at the injection site).

Adverse Event of Special Interest (AESI):

An AESI is an event for which ongoing monitoring and rapid communication by the Investigator to the Sponsor must be done. Such an event might warrant further investigation in order to characterize and understand it. Depending on the nature of the event, rapid communication by the study Sponsor to other parties (e.g., regulators) might also be warranted.

Medically-Attended Adverse Event (MAAE)

A MAAE is defined, for the purpose of this study, as a new onset of a condition that prompts the subject or subject's parent/guardian to seek unplanned medical advice at a health care provider's office or Emergency Department. This definition excludes pre-planned medical office visits for routine pediatric check-ups or follow-up visits of chronic conditions with an onset prior to entry in the study. Health care provider contact made over the phone or by email will be considered a physician office visit for the purpose of MAAE collection. The outcome of the health care provider contact (whether it results in a prescription or not) will not be considered as a basis for reporting the event as an MAAE and all contacts should be reported. Sufficient data should be collected for the event to allow an assessment of the causality and diagnosis, if possible.

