4.4.2.2.4 Time of Onset

Time of onset is derived from the start date of the unsolicited AE and the date of last vaccination as described in [Section 4.4.2.2.3](#):

Time of Onset = start date of the unsolicited AE - date of last vaccination before the unsolicited AE (if D0 is the first vaccination day).

The time of onset is considered as missing only if one or both dates are missing or partially missing.

The unsolicited AEs will be analyzed “Within 30 days” after each vaccination, which corresponds to AEs with a time of onset between day 0 and day 30.

Unsolicited AE that occurred before vaccination (negative time of onset) will not be included in analysis but will be listed separately.

Unsolicited AE which is non-serious, non-AESI and non-MAAE that occurred with a time of onset higher than defined above will not be included in analysis but will be listed separately.

- For unsolicited AE with missing day, month and year, the unsolicited AE will be classified as “Within 30 days”
- For unsolicited AE with partially missing start date, the partial available information will be used to determine if this AE is classified “Within 30 days” or “Not within 30 days”. An AE will be categorized as “Not within 30 days” only if there is clear evidence from the

partially missing start date that this AE happens before the first vaccination or after the last vaccination + 30 days. In all other situations, this AE is considered as “Within 30 days”. Situations may happen as:

- If the start date of AE has missing Day and non-missing Month and Year
 - If the “Month/Year of AE start date” < “Month/Year of first vaccination date”, then it is clear that this unsolicited AE happened before the first vaccination and this unsolicited AE will not be included in the analysis but will be listed separately.
 - Else if the “Month/Year of last vaccination date” <= “Month/Year of AE start date” <= “Month/Year of (last vaccination date + 30 days)”, then this unsolicited AE will be categorized as “Within 30 days”.
 - Else if the “Month/Year of AE start date” > “Month/Year of (last vaccination date + 30 days)”, then this unsolicited AE will be categorized as “not within 30 days”. If the AE is non-serious, non-AESI and non-MAAE, then it will not be included in the analysis but will be listed separately.
- If the start date of AE has missing Day and Month and non-missing Year:

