4.4.2.4 Medically-Attended Adverse Event (MAAE)

An event will be considered as an MAAE if “Yes” is checked for “Is the event an MAAE?” in the CRF.

MAAEs will be analyzed throughout the study using the following periods:

- During the entire study period after any dose from D0 to last phone call (i.e., all MAAEs that occurred during the study)
- From Day 0 to Day 30 after each vaccination

A MAAE with missing time of onset will be considered to have occurred just after the vaccination indicated by the visit number, so will be included in the safety analysis tables mentioned above.

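### The MAAE definition covers only new-onset conditions, so an unplanned visit for a non-serious worsening after Day 30 enters no safety summary table and may be classified differently between sites

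*Protocol*

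**What the plan says.** **MAAE definition.** Protocol 9.3.2.1 defines an MAAE "as a new onset of a condition that prompts the subject or subject's parent/guardian to seek unplanned medical advice". SAP 4.3.1.1 repeats it: "A MAAE is defined, for the purpose of this study, as a new onset of a condition". Both then exclude pre-planned routine check-ups and "follow-up visits of chronic conditions with an onset prior to entry in the study". Neither mentions an unplanned visit for a worsening.

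**AE definition.** The same Protocol section makes it a reportable AE (an exacerbation) "if a pre-existing medical condition worsens following study interventions in frequency or intensity". It applies this to recurring episodes too, with asthma as the example.

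**Windows.** Protocol 9.3.2.2 sets the general endpoint as the occurrence "of unsolicited AEs up to D30 after each vaccination". SAP Table 4.1 gives the same Day 0 to Day 30 window. Only SAEs (including AESIs) and MAAEs run from Visit 1 to the 6-month contact.

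**Later events.** SAP 4.4.2.2.4 states: "Unsolicited AE which is non-serious, non-AESI and non-MAAE that occurred with a time of onset higher than defined above will not be included in analysis". The sentence goes on to say that these events are listed separately.

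**Classification.** SAP 4.4.2.4 begins "An event will be considered as an MAAE if" and completes the rule with a Yes tick on the CRF. It has no rule for exacerbations.

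**The concern.** The two definitions in Protocol 9.3.2.1 do not cover the same ground. Worsening counts for an AE, but the MAAE wording admits only a new onset. The difference matters because, beyond Day 30 after a dose, MAAE is the only endpoint that summarises non-serious events.

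Aggravation of an existing condition is one plausible form of harm from a vaccine. Under the literal wording, the MAAE percentage for the whole study understates unplanned medical contacts, because it leaves out those prompted by a worsening. Within Day 0 to 30 such a visit still counts as an unsolicited AE but is absent from the separate Day 0 to 30 MAAE summary.

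There is also a consistency problem. The exclusion sentence names only routine check-ups and chronic-condition follow-up visits. One site may tick Yes for an unplanned visit for a flare and another may not. The reported percentage would then mix two definitions.

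**Working it through.** The documents state no figure for this point, so there is none to reproduce. The check has two parts.

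**1. Tracing one event.** Take a child with a condition present before entry who is taken, unplanned, to a doctor for a non-serious, non-AESI worsening that starts after Day 30 following a dose.

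- AE? Yes (Protocol 9.3.2.1, AE definition).
- SAE or AESI endpoint? No, by construction.
- Unsolicited AE endpoint? No. The window ends at Day 30 (Protocol 9.3.2.2, SAP Table 4.1).
- MAAE endpoint? Not on the literal wording, because it is not a new onset.
- Any other table? Only if it led to discontinuation, through the disposition or safety overview tables (SAP 4.4.2.5.5).
- Listing? Yes, if it was recorded (SAP 4.4.2.2.4).

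Whether it is recorded depends on when it happens:

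- *Between doses:* it may be. Protocol 5.1.1 says "unsolicited AEs will be collected from D0 after each vaccination to the next study visit", and 9.3.2.3 has staff ask at each visit about other AEs since the previous one. The Table of Study Procedures, however, gives Day 0 to Day 30 for recording unsolicited AEs.
- *After the last visit:* possibly not. The memory aid is for SAEs (including AESIs) and MAAEs only (Table of Study Procedures footnote for Groups 1 and 2; Protocol 5.1.4.2 for Groups 3 and 4). The final call asks only about SAEs and MAAEs (Protocol 5.1.4.1 and 5.1.4.2).

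**2. Share of follow-up outside the Day 0 to 30 windows.**

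Inputs from the Tables of Study Procedures: dose interval at least 6 months (Groups 1 and 2) or at least 3 months (Groups 3 and 4); final contact 180 days after dose 2, window +30 days. Assumption: one month is 365.25/12 days, rounded to whole days, which gives 183, 213, 91 and 122 days for 6, 7, 3 and 4 months.

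Formula: total days = interval + follow-up after dose 2 + 1. Days covered = 2 × 31 = 62. Share outside = (total − 62) / total.

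| Groups | Interval | After dose 2 | Total | Outside | Share |
|---|---|---|---|---|---|
| 1 and 2, shortest | 183 | 180 | 364 | 302 | 83.0% |
| 1 and 2, longer | 213 | 210 | 424 | 362 | 85.4% |
| 3 and 4, shortest | 91 | 180 | 272 | 210 | 77.2% |
| 3 and 4, longer | 122 | 210 | 333 | 271 | 81.4% |

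These are shares of time, not of events. The documents give neither the frequency of existing conditions nor the rate of unplanned visits for worsening, so the number of affected events cannot be computed.

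**The case against.** The strongest reply is that little is really lost.

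- **Listing.** Late events are kept out of the analysis but listed separately, and between doses they should often be recorded. A reader might infer that they vanish from the report. The documents do not support that for recorded events. It remains possible after the last visit, where the tools do not ask for them.
- **Graver cases are covered.** Hospitalisation makes an event an SAE. Protocol 9.3.2.1 gives bronchospasm needing intensive treatment, in an emergency room or at home, as an important medical event. What remains is mainly milder outpatient worsening. This stands.
- **Conditions that begin after dose 1.** A reader might include these in the gap. The first presentation that prompts unplanned advice is a new onset, so it is an MAAE.
- **The literal reading may not be intended.** Excluding follow-up visits of chronic conditions would be redundant if new onset already removed every visit for an existing condition. The definition also says that all contacts should be reported, although that sentence concerns whether the outcome of the contact matters. This supports calling the text ambiguous. It does not settle how sites will tick the box. The CRB completion instructions might, but they are not among the documents.
- **Impact.** Safety is descriptive, the definition is the same in every group, and assessment is under modified double-blinding. A reader might infer bias between groups. Nothing in the documents points to one.

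**Conclusion.** The gap in the wording is real, and its consequence follows from stated rules. Read literally, an unplanned visit for a non-serious worsening with onset after Day 30 enters no safety summary table. It is at most listed, unless it led to discontinuation, and after the last visit it may go unrecorded. Where sites read the definition more broadly, the result is inconsistent capture.

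The period exposed is about 83% of follow-up in Groups 1 and 2 and 77% in Groups 3 and 4, at the shortest dose intervals and a 180-day final contact. Longer intervals or later calls raise both shares. A reader might take these as the fraction of events missed, or attach outside rates to get a number of children. The documents support neither.

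The effect is on the absolute, descriptive MAAE rate. No hypothesis test is affected. Severity: minor.

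**What to change.** **If collection continues.** In Protocol 9.3.2.1 and SAP 4.3.1.1, widen the definition from a new onset of a condition to a new onset or a worsening of one, where it prompts unplanned medical advice. Keep the exclusion of pre-planned check-ups, and state that chronic-condition follow-up visits are excluded when planned. Carry the same wording into the CRB completion instructions, diary card and memory aid, so that the CRF tick means the same at every site.

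**If collection is complete.** SAP 5.6 describes the data review in the past tense, so this may apply. Tabulate, by group, the recorded AEs with onset after Day 30 that have health care provider contact as the action taken (a category in Protocol 9.3.2.3.3) and are not flagged as MAAEs. State that events after the last visit may not have been recorded. A change to the SAP cannot recover those.

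**Cost.** A phrase in two documents, handled under Protocol 5.4, and an updated instruction to about 30 sites. No visit or procedure is added. The reported MAAE rate would be slightly higher. If the change is made partway through, the report should give its date, because earlier events were collected under the narrower wording.
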